Study Population and Main Eligibility/ Exclusion Criteria:	
Inclusion Criteria:
 
 • Healthy volunteers, free from symptoms of orthostatic intolerance and without any chronic medical condition 
 ○ Non-smoking ○ Free of medications with the potential to influence blood pressure (BP) ○ Age between 18-60 years ○ Male and female participants are eligible ○ Able and willing to provide informed consent • Patients diagnosed with POTS by the Vanderbilt Autonomic Dysfunction Center based on the following stringent criteria: 1) history of daily orthostatic symptoms for at least 6 months; 2) increase in heart rate (HR) of at least 30 bpm with standing or a standing HR \geq 120 bpm; 3) absence of orthostatic hypotension (defined as a fall in BP $> 20/10$ mm Hg); and 4) absence of conditions, such as dehydration, substantial weight loss, or systemic illnesses, that could provoke orthostatic intolerance 
 ○ Non-smoking ○ Free of medications with the potential to influence BP

	
 ○ Age between 18-60 years ○ Male and female participants are eligible ○ Able and willing to provide informed consent 
Exclusion Criteria:
 
 • Overt cause for postural tachycardia (such as acute dehydration) • Significant cardiovascular, pulmonary, hepatic, or hematological disease by history or screening results • Positive urine b-hcg pregnancy test or breastfeeding • Evidence of cardiac structural disease (by clinical examination or prior echocardiogram) • Hypertension defined as a BP>145/95 (off medications) or need for antihypertensive medications • Evidence of significant conduction system delay (QRS duration >120 ms) on electrocardiogram • Known allergy to FD&C Yellow dye 6 • Inability to give, or withdraw, informed consent • Other factors which in the investigator's opinion would prevent the participant from completing the protocol, including poor compliance during previous autonomic studies or an unpredictable schedule • Participants in the dose escalation part of the study are excluded from participation in the main study.
Primary Outcome Measures:	For the dose escalation study, results from the labs, ECG, Psychiatric Questionnaire and vital signs will be evaluated. For the main study, the primary outcome is the urinary sodium concentration normalized to creatinine.

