- Supine heart rate and blood pressure will be measured and supine blood samples will be collected hourly for 4 hours after the last dose and at 8 hours after the treatment. Participants must rest supine for at least 30 minutes before each blood draw. The intravenous catheter will be removed following the 8-hour blood draw.
- At 2 hours after the 5th dose, participants will stand for 10 minutes for upright blood pressure and heart rate measurements and collection of an upright blood sample, as described above. Participants will be asked to rate the severity of common orthostatic symptoms while supine and upright.
- Urine will be collected for two 4-hour periods after the last dose followed by a 16-hour collection to finish the 24-hour cycle.
- Participants may be discharged approximately 8 hours after the last dose or, if they prefer, they may remain on the CRC for the washout day(s).
- Fixed-sodium and low monoamine and methylxanthine-free study diet will be provided after the 4-hour measurements and in the evening.

After at least a 1 day washout period, the study will be repeated with Treatment B

2. Objective and Research Question of the Main Study

Specific aims.

1. To assess normal changes in plasma and urinary levels of catecholamines following oral carbidopa administration.

We are giving 200mg of carbidopa every 6 hours for 5 doses. We expect that this treatment will decrease the formation of dopamine in the kidney so that urinary dopamine will be lowered and its precursor, urinary dopa, will be raised.

2. To assess the relationship between catecholamines and urinary sodium excretion following oral carbidopa administration.

Because of the important role of kidney dopamine in regulating urinary sodium excretion, we expect that urinary sodium excretion will be decreased as urinary dopamine falls.

3. To assess the effect of oral carbidopa administration on orthostatic changes in heart rate and blood pressure, as well as symptoms.

Because of the relationship between sodium excretion and blood pressure control, we expect that a carbidopa-mediated decrease in urinary sodium excretion may be associated with an increase in blood pressure.

4. To compare the catecholamine, diuretic, and cardiovascular responses following orally administered carbidopa in participants with POTS with those of healthy volunteers.

One of the most consistent findings in POTS is a reduction in plasma volume or blood volume.

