paradoxically low in POTS in view of the reduced plasma volume. This indicates that sodium handling is perturbed in POTS. Several investigators have implicated dopamine in the control of natriuresis in other disorders. Approximately 50% of sodium excretion appears to be under dopaminergic regulation.

Uptake of dopa into the proximal tubule cells and its subsequent decarboxylation to DA are stimulated by a high salt diet. Carbidopa inhibits the activity of AADC in the periphery. By blocking the conversion of dopa to DA, it has the potential to attenuate the effects of the sodium load on renal DA production and urinary sodium excretion. However, since carbidopa also inhibits dopa decarboxylation in peripheral neurons, it can increase plasma dopa levels and the filtered load of dopa in the kidney. The final effect of carbidopa on renal DA production is therefore the result of increased substrate and decreased decarboxylation[12].

Recommended dosages of carbidopa for the treatment of Parkinson's disease, as Sinemet®, are at least 70-100 mg, up to 200 mg daily (AHFS Drug Information 2007). Yet, Durso et al.[6] speculated that "doses used in current practice" are not saturating for the decarboxylase enzyme. Kaufmann et al.[22] and Hershey et al.[15] administered one dose of 200 mg carbidopa to ensure that the decarboxylase was completely inhibited. Stokes et al.[30] proposed that more than one dose of carbidopa must be given to see an effect on renal salt handling. Based on this information and a carbidopa half-life of about 2 hours, we have chosen to administer 200 mg of carbidopa every 6hr. We believe that with repeated dosing of 200 mg, we will be able to assess the influence of decarboxylase inhibition on urinary sodium excretion. Nevertheless, since this dosage is higher than that which is FDA approved, we will first conduct a dose escalation study with 50mg, 100mg and 200mg of carbidopa to confirm that these dosages are well tolerate

[figure not shown]
[figure not shown]

Figure 3

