As much as possible data quality is assessed at the data entry point using intelligent on-line data entry via visual basic designed screen forms. Data element constraints, whether independent range and/or format limitations or 'relative' referential integrity limitations, can be enforced by all methods employed for data input. QA reports assess data quality post-data entry. As we note, data quality begins with the design of the data collection forms and procedures and incorporates reasonable checks to minimize transcription and omission errors. Of the more important quality assurance measures are the internal validity checks for reasonableness and consistency.

[figure not shown]
- Data Monitoring: The RDCRN DMCC identifies missing or unclear data and generates a data query to the consortium administrator contact.
- Data Delinquency Tracking: The Data Management and Coordinating Center will monitor data delinquency on an ongoing basis.

6. Statistical Considerations

Individual data will be reviewed for the Dose Escalation Study with the post-dose data compared to pre-dosing data. The data for each cohort will be summarized for review by [name] and the IMM of this study. The primary outcome is the urinary sodium concentration normalized to creatinine. Differences in urinary sodium in samples (1) collected at baseline vs. those collected following treatment (time effect) and (2) collected after placebo vs. carbidopa (treatment effect) will be assessed using a paired t-test and Wilcoxon signed-rank test. Differences between the patient and control groups (group effect) will be assessed using a student's t-test and a Mann-Whitney U test. Similar methods will be used to compare secondary outcome measures, such as BP, HR, plasma and urinary catecholamines, plasma renin activity, plasma aldosterone, and plasma sodium. All data analyses will be performed using SPSS 18.0 (SPSS, Chicago, IL) or STATA 8.2 (StataCorp, College Station, TX). All statistical tests will be two-sided. A mixed-effects model will be developed to describe the time, medication and group effects.

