Sample Size Calculation. Based on our preliminary findings of a standard deviation for urinary sodium excretion of 30 mEq/g creatinine, a sample size of 16/group (32 total) will have 80% power to detect a difference in group means (control vs. POTS) of 31 mEq/g creatinine with a 0.05 two-sided significance level. To allow for participant drop-out prior to study completion, we will plan to obtain informed consent from 35 participants in total (18 POTS, 17 healthy controls).

Randomization procedures were performed by [REDACTED] and the results provided to Vanderbilt's Investigational Pharmacy. Prior to admission, the pharmacy is notified whether the participant is a patient or healthy volunteer and the Investigational Pharmacist determines the treatment order (placebo or carbidopa first). At the end of the study, the blinding will be broken by the Vanderbilt Investigational Pharmacy and the order of agents will be revealed to the investigators and to the participants, if they so request.

7. Data Management

The investigators, research personnel and nursing staff at the CRC will collect the majority of the data at the bedside in real time. Data will be handwritten on CRFs provided by [name]. Routine labs are sent to

the hospital laboratory for analysis. Special study specific labs (ex: catecholamines) are sent to the GCRC Core Lab for analysis. Laboratory data will be obtained from Vanderbilt Medical Center's online medical chart system (StarPanel) and from the GCRC Core Laboratory website, both of which are password protected and only authorized personnel have access. After all data points have been retrieved, a member of the research team will enter the data into the DMCC database, which is also password protected and only accessible to authorized personnel. Data analysis will be performed routinely for periodic review. Hard copies of the CRFs will be maintained in the patient's research chart in a locked cabinet. Study participation will be complete following the inpatient evaluation. There will be no further study follow-up. Study records will be kept for at least 7 years following the publication or presentation of the data collected as part of this study.

All study data will be collected via systems created in collaboration with the RDCRN Data Management and Coordinating Center and will comply with all applicable guidelines regarding patient confidentiality and data integrity.

7.A Registration

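### The primary outcome has no named urine collection, contrast or test, and three sections point to three different deciding questions, so the single 0.05 test behind the sample size is not defined

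*Combined protocol and SAP*

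**What the plan says.** **Outcome.** For the main study, "the primary outcome is the urinary sodium concentration normalized to creatinine" (Synopsis, Primary Outcome Measures; repeated in Section 6). Neither place gives a collection or time point.

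**Collections (Sections 1.C, 4.G and 4.H).** Each period starts with a 24-hour baseline collection. The day of doses 1 to 4 is collected either as one 24-hour sample or as 4-, 4- and 16-hour samples. After dose 5, "Urine will be collected for two 4-hour periods after the last dose followed by a 16-hour collection". Discharge is allowed about 8 hours after dose 5.

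**Tests (Synopsis, Statistical Considerations; Section 6).** Time effects (baseline against post-treatment) and treatment effects (placebo against carbidopa) "will be assessed using a paired t-test and Wilcoxon signed-rank test". Group effects get a Student's t-test and a Mann-Whitney test. "All statistical tests will be two-sided". No order of importance or multiplicity rule is given. A mixed-effects model follows: in the Synopsis only if the earlier analyses suggest that the carbidopa response differs between groups, in Section 6 without that condition.

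**Deciding question.** The Synopsis makes carbidopa against placebo the primary objective and the patient-control comparison secondary. Section 2 states one null hypothesis: that the carbidopa effect on sodium excretion is equal in POTS and healthy volunteers. The sample size in Section 6 rests on "a standard deviation for urinary sodium excretion of 30 mEq/g creatinine" and "will have 80% power to detect a difference in group means (control vs. POTS) of 31 mEq/g creatinine", "with a 0.05 two-sided significance level".

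**The concern.** A study that is sized for one test at 0.05 has to say which test that is. Here three choices stay open: which urine collection, which contrast, and parametric or rank test. Whoever analyses the data could report whichever combination is significant as the primary result and still be following the text. The error rate of that result would not be 5%, and the 80% power would belong to a comparison that may not be the one reported.

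The collections also differ in their relation to dosing, so the choice of window can change the size of the estimated effect as well as its p-value.

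**Working it through.** **1. The plan's own figure.** Inputs from Section 6: difference 31, SD 30, two-sided 0.05, 16 per group. Noncentrality = 31 / (30 × √(2/16)) = 31 / 10.61 = 2.92 on 30 degrees of freedom, which gives 80.7% power. The stated 16 per group reproduces. The arithmetic is sound for one two-sample comparison of means.

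**2. Candidate primary values per period.** Doses 1 to 4: 1 or 3 collections. After dose 5: 3. The total is 1 + 3 = 4 or 3 + 3 = 6 post-dose collections (5 or 7 with baseline). With three contrasts and two tests each, the text covers 4 × 6 = 24 or 6 × 6 = 36 p-values for the primary outcome, before the mixed model.

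**3. Treatment contrast alone, any window counting.** If the windows were independent, the chance of at least one p < 0.05 under no effect would be 1 − 0.95⁴ = 18.5% or 1 − 0.95⁶ = 26.5%. Windows from one person are correlated, so I simulated the paired t-test under no effect with 32 participants. The assumed correlation between windows was 0.3 to 0.7.

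| Post-dose windows | Chance of at least one p < 0.05 |
|---|---|
| 1 | 5% |
| 4 | about 13 to 18% |
| 6 | about 16 to 24% |

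Allowing either the t-test or the Wilcoxon test adds only about 2 to 4 points, because the two are highly correlated.

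**4. One window, one test each, three co-equal contrasts.** 1 − 0.95³ = 14.3% if independent; 13 to 14% by simulation.

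**5. Are the windows equivalent?** Section 3 gives "a carbidopa half-life of about 2 hours". The final 16-hour collection starts 8 hours after dose 5, which is 8/2 = 4 half-lives, so 0.5⁴ = 6.25% of the drug remains by plasma level. That collection is 16/24, or two thirds, of the last cycle. The documents do not say how long the effect on decarboxylase or on sodium handling lasts.

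**6. What the choice does to power at 16 per group, for a difference of 31.**
- One contrast of group means, one window, one test: 80.7%.
- Three co-equal contrasts with Bonferroni (0.05/3 = 0.0167): 65% for the group-mean contrast; 80% needs 22 per group.
- The Section 2 hypothesis, comparing groups on the within-person carbidopa-minus-placebo difference. If 30 is the SD of a single measurement, the SD of the difference is 30 × √(2(1 − ρ)). The documents do not give the within-person correlation ρ:

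| ρ (assumed) | SD of difference | Power at 16 per group | n per group for 80% |
|---|---|---|---|
| 0 | 42.4 | 52% | 31 |
| 0.3 | 35.5 | 67% | 22 |
| 0.5 | 30.0 | 81% | 16 |
| 0.7 | 23.2 | 95% | 10 |

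**The case against.** The plan is not without priorities. It has a ranked objective, a single stated null hypothesis, and a level and power tied to one contrast. The Synopsis wording on the mixed model suggests that the group test may have been meant for the response to carbidopa. That model is also a joint analysis, which partly answers a complaint about separate tests. The optional split on the first dosing day has a stated purpose, matching clock times with the collection after the last dose, and need not mean six primary tests.

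These points are fair but do not supply a deciding analysis. The objective, the hypothesis and the sample size name three different questions. The group test does not say which quantity is compared. The model names no deciding coefficient or window, and the two descriptions disagree on whether it is always fitted.

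A reader might go further and infer that the plan's false-positive rate is 30 to 50%. Pooling all three contrasts over every window by t-test does give about 32 to 40% (four windows) and 39 to 52% (six) under assumed correlations. The documents do not support that as the plan's error rate. The 0.05 level appears only in the sample-size text, and no section says that any significant contrast makes the study positive. Time, treatment and group effects are separate questions, so a chance group difference is not a false carbidopa claim. The six-window figures also require every participant to have followed the optional split schedule.

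**Conclusion.** The point holds. The plan names no deciding collection, contrast or test for the primary outcome, and its sections disagree on the deciding question. The single 0.05 test for which 16 per group was calculated is therefore undefined, although the sample-size arithmetic is correct.

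The size is illustrative: about 13 to 18% (four windows) or 16 to 24% (six) for the treatment contrast alone, and about 14% for three contrasts on one window, instead of 5%. The window figures rest on assumed correlations of 0.3 to 0.7, and all of the figures on any significant result being counted, which the documents neither state nor exclude. The choice of rank or t-test contributes little; windows and contrasts contribute most.

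A reader might also infer from the half-life that the last 16-hour sample is off drug, or that the effect has reversed by then. The 6% is a plasma level, and the documents do not equate it with duration of effect. Section 3 cites a proposal that repeated doses are needed before renal salt handling changes, so effect need not track concentration. What follows is only that the windows cannot be assumed equivalent. That is enough reason to choose one in advance.

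**What to change.** Before unblinding:

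1. Reconcile the Synopsis objectives, the Section 2 hypothesis and the Section 6 analysis and sample size, and state one deciding contrast. State also whether the mixed model is always fitted and what role it has.
2. Name one collection window that exists for everyone. One option is 0700 Day 1 to 0700 Day 2, with split samples pooled as total sodium over total creatinine. It is inpatient and available under either schedule, but it includes the hours after the first dose. The other is the two 4-hour samples after dose 5 combined, which follows repeated dosing but covers only 8 hours.
3. Name one test. Keep the rank test as a sensitivity analysis.
4. Report the other windows and contrasts as secondary estimates with confidence intervals.
5. If the Section 2 hypothesis is chosen, restate the power for that contrast, with the assumed within-person correlation and what the SD of 30 refers to.

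This needs SAP wording and no new procedures. The downside is that the other windows and contrasts become secondary. Under the Section 2 hypothesis, 16 per group may prove too few if the within-person correlation is below about 0.5.
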